## 4.4 Study Procedures

**A. Recruitment and Informed Consent.** The Office of Community Outreach (OCO) has a history of working with multiple community organizations, offering free bilingual education via our community speakers bureau. During our education sessions, community partners coordinate logistics, promote our programs and invite community members to participate. Recruitment of study participants will occur working through these long-standing community partners. Partner sites will promote the study and invite participants to a session to learn more. A recruitment flyer may be used at some sites to advertise the study.

Recruitment efforts will be concentrated in census tracts with the greatest need for intervention, i.e., census tracts identified as high-risk due to socioeconomic factors linked to liver cancer (e.g., % non-Hispanic Black, household stability) and high rates of liver cancer. If no current partners are located in these high-risk census tracts, potential new partners will be identified by searching for community centers, federally qualified health centers, etc.

Individuals who attend the session will be informed about the scope of the study and invited to formally participate by the study team. Individuals interested in participating will be consented by health educator [name], project manager [name], or Co-PI [name] prior to completing the pre-intervention survey. Persons not interested will be thanked for their time and excused. We anticipate recruiting between 50-100 participants, depending on the number of participating community partners and the number of education session completed. Education sessions may be conducted on a one-on-one basis or in a group, depending on the number of interested individuals present at any given session. Individuals who refuse to participate or who withdraw from the project will be treated without prejudice.

Due to the COVID-19 pandemic, in-person recruitment efforts conducted by OCO has ceased. During pandemic-related closures, all study-related activities will be conducted over the phone, online, and through US mail. Recruitment will be conducted over the telephone, and informed consent will be obtained verbally (also over the telephone). Once informed consent is obtained, an oral consent document will be sent via US mail to the participant.

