#### **B. Study Survey**

Once eligibility has been confirmed, informed consent has been obtained, participants will fill out a sign-in sheet that includes their street address. If the participant agrees to be contacted about this or future research after their participation, they will also be asked to write their telephone number on this form. Because the sign-in sheet contains identifiable information, it will be kept separate from survey data and will be linked by a study ID assigned to the participant after consent. The street address data will be geocoded for neighborhood analysis. Telephone numbers will be stored in a secure database. Once geocodes are created from the street addresses, hard copies of the sign-in sheets will be destroyed. After the sign-in sheet is collected, the study survey will be administered. Once approved, the English survey will be translated into Spanish language. Once translated, a modification will be submitted.

The study "pre" survey will be administered post informed consent process and prior to the educational intervention by OCO health educators (field staff). Upon completion of the educational module, a posttest survey will be administered. All survey data will be entered in the RedCap database.

Both the pre- and post-survey will contain measures of knowledge about liver risks and prevention, self-efficacy about talking to medical professionals about neighborhood risk, as well as demographic items (e.g. gender, race/ethnicity). The post survey will include similar knowledge questions as well as additional questions specifically related to neighborhood health, including a program evaluation, outcome expectancies about learning about neighborhood health (i.e., the extent to which leaning about neighborhood health will be beneficial), and intentions to talk with clinicians about liver cancer, neighborhood health and liver cancer screening. **Primary outcomes** include pre-post changes in knowledge about liver cancer, interest in learning about neighborhood health, outcome expectancies for learning about neighborhood health, and participant intentions for talking to their doctors about liver cancer risk.

During COVID-19 closures, the survey will be administered over the telephone. Mailing and street address will be collected during recruitment, so that informed consent copies and intervention materials can be mailed to the participant.

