#### 6.0 Risks to Participants

For this study, in Aim 1, we will be utilizing existing data resources under a currently approved IRB protocol #17-9031. Only geocoded (census tract level), de-identified data will be used for analysis. We will provide additional protections for our deocoded study populations as follows. If we are provided patient addresses, we will employ a "false coordinate system" to decouple household addresses from individual personal data attributes. That is, we will map the data in such a way that the true geographic location is not stored in the GIS software. For instance, the actual position of an address might be described by the coordinates: -125.652, 24.229 (see the illustration below). The statistical tools within GIS enable us to very simply alter the true coordinate values by adding or subtracting a fixed value to all the X and Y geographic coordinates in the dataset. We intend to employ a "minimum-maximum false coordinate range" of values 1-8 — to ensure that the confidentiality of the study participants' household addresses are, not in any way, compromised. Further, for areas or census tracts with a minimal number of patients (i.e. <6 patients), we will employ geographic aggregation and geomasking techniques to further protect confidentiality[14, 16] Given we are working with geocoded, de-identified registry data for analysis and employing patient protections during the collection, storage, and analysis of data, this study represents minimal risk to participants.

There is no physical risk to participants. There is a however a small risk that participant(s) may feel uncomfortable answering some questions on the survey. Participants will be informed of their options to not answer any question they are uncomfortable responding to.

The study team will make every effort to keep the information provided in the study confidential.

- All information gathered during this study will be kept in locked cabinets or in electronic databases that are password-protected.
- The study team will delete your name and other information that might identify participants, whenever possible.

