# 14.0 Statistical Analysis

**14.1 Spatial Analysis**. The dataset for the geospatial analysis is de-identified, and geospatially aggregated to protect patient confidentiality[14]. Spatial analyses will be conducted by Fox Chase Cancer Center/Temple University using SatScan spatial scan statistics that empirically identify neighborhood clusters at the census tract level wither higher than expected rates of liver cancer [17], similar to existing protocol #17-9031. Mapping will be completed using ArcGIS 10.2 software (www.esri.com).

**14.2 Participant Self-Report Data.** Demographics will be summarized using descriptive statistics. Statistical analysis for efficacy of the education sessions will include changes in knowledge, changes in self-efficacy, and intention. Mean differences will be calculated in self-report outcome measures at pre- and post-survey, along with standard deviations and the effect size (mean difference/SD of the differences). We will compare the pre-post differences using t-tests or Wilcoxon tests, as appropriate.

**14.3 Power**. The sample size calculations are based on the primary outcomes for the pre-post evaluation of the education intervention. We assume a standard effect size of 0.3-0.4 on the primary outcomes (0.3-0.4 times the standard deviation of the pre-post changes for the

measures). We therefore aim to accrue up to 100 patients (but no less than 50) to have 80% power to detect a standard effect of 0.3-0.4, with 5% two-sided type-I error.

**14.4 Limitations**. Modifiable area unit problem (MAUP) will be evaluated and appropriate scale, aggregation, and cluster size will be considered for geospatial analysis.

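### Does section 14.3 overstate power by giving 80% for effects of 0.3-0.4 across 50 to 100 participants?

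*Combined protocol and SAP*

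**What the plan says.** Section 14.3 assumes a standardised effect of 0.3 to 0.4 on the primary outcomes, where the unit is the standard deviation of the within-person change. From this it concludes that the investigators "therefore aim to accrue up to 100 patients (but no less than 50) to have 80% power to detect a standard effect of 0.3-0.4". The significance level is 5%, two-sided.

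Section 4.4 A gives the same range and says what decides the final number: "We anticipate recruiting between 50-100 participants, depending on the number of participating community partners and the number of education session completed".

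On the analysis, section 14.2 says: "We will compare the pre-post differences using t-tests or Wilcoxon tests, as appropriate". It also commits to reporting the mean change, standard deviations and the standardised effect.

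Three other statements bear on how many usable pairs there will be. Under section 4.4 B the primary outcomes "include pre-post changes in knowledge about liver cancer, interest in learning about neighborhood health, outcome expectancies for learning about neighborhood health", together with intentions to talk to a doctor about liver cancer risk. The same section says: "The post survey will include similar knowledge questions as well as additional questions specifically related to neighborhood health". Section 6.0 adds: "Participants will be informed of their options to not answer any question they are uncomfortable responding to".

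**The concern.** Two ranges share one power figure, so the sentence can be read as promising 80% power for 0.3 at every permitted size. That would be false. A study that closes at 50 complies with the protocol, since the number of partners and sessions settles the size, and section 4.1 reports that the pandemic had already hampered recruitment. At 50 pairs and a true change of 0.3, the chance of missing it on a given outcome is about 45% rather than 20%. A null result at the floor could then be taken as stronger evidence against a modest benefit than it is.

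Two further points seem to make this worse. The Wilcoxon test needs somewhat more pairs if the differences are normal. Also, the section counts people accrued, whereas power depends on complete pre-post pairs.

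**Working it through.** **Inputs, all from section 14.3.** Two-sided alpha 0.05; power 80%; standardised effect d = 0.3 to 0.4; size n = 50 to 100. Because d is in units of the SD of the change, this is a one-sample calculation on the differences and no pre-post correlation is needed.

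**Step 1: reproduce the plan's range.** Normal approximation: n = ((1.960 + 0.842)/d)², with (2.802)² = 7.851.

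- d = 0.40: 7.851/0.16 = 49.1, so 50.
- d = 0.35: 7.851/0.1225 = 64.1, so 65.
- d = 0.30: 7.851/0.09 = 87.2, so 88.

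The floor of 50 is exactly the rounded-up requirement for 0.4. The ceiling of 100 covers the requirement for 0.3 with 12 to spare.

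**Step 2: t-test power.** Noncentral t with n − 1 degrees of freedom and noncentrality d√n. For example, 0.4 × √50 = 2.828, 0.3 × √50 = 2.121 and 0.3 × √100 = 3.000.

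| n | d = 0.30 | d = 0.35 | d = 0.40 |
|---|---|---|---|
| 50 | 54.8% | 67.9% | 79.2% |
| 75 | 72.7% | 84.9% | 92.8% |
| 90 | 80.4% | 90.7% | 96.4% |
| 100 | 84.4% | 93.4% | 97.7% |

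Pairs needed for 80%: 52 at 0.40, 67 at 0.35 and 90 at 0.30. At d = 0.30, n = 89 gives 79.9%.

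**Step 3: invert the question.** The effect detectable with 80% power is 0.404 at n = 50, 0.328 at n = 75 and 0.283 at n = 100. So as n moves over the permitted range, the detectable effect moves from about 0.40 to just under 0.30. That is what section 14.3 says when its two ranges are read together.

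**Step 4: where the 55% comes from.** It is the top-left cell of the table: smallest size, smallest effect. It is arithmetically right, but the plan does not assert it.

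**Step 5: the Wilcoxon test.** Simulation with normal differences gives 52.7% at n = 50, d = 0.30 (2.1 points below the t-test) and 77.4% at n = 50, d = 0.40 (1.8 points below). Reaching 80% takes about 95 pairs at 0.30 and about 54 at 0.40, both inside the permitted range. Normality is an assumption here, since the documents give no distribution. An analyst would usually turn to Wilcoxon when the differences are not normal, so these figures describe the case where it is least likely to be used.

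**The case for a change.** The best case for a change is that an implied pairing does not control where the study stops. Logistics decide the size, 0.3 is one of the plan's own planning values, and every size from 50 to 89 falls short of 80% at 0.3. One added sentence would cost nothing and would spare readers the inference.

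The facts in this stand: ending at 50 is permitted, and power for 0.3 there is about 55%. But the sentence sets 50 as a minimum and aims for up to 100, where 0.3 is covered. Section 4.3 A describes the work as a pilot, and it has a single group. The results will show the observed standardised effect and its SD, so a reader can judge precision at the size actually reached. No enrolment, test or decision would differ if the pairing were spelled out.

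The point about complete pairs is true in general but unquantified. Under the in-person design the two surveys sit either side of one session, and section 4.4 C expects no active follow-up, so losses may be small. Telephone or mailed delivery could separate the surveys, but no missingness rate is given. Whether some primary outcomes are asked only after the session is a question of endpoint definition. It depends on the survey in Appendix C, which is not in the text reviewed, and it does not show a sample-size error.

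**Conclusion.** The concern does not call for a change. Section 14.3 is compressed rather than wrong: its two ranges pair inversely, about 50 with 0.4 (79.2% power; 52 pairs for a full 80%) and about 90 to 100 with 0.3 (80.4% to 84.4%). The shortfall of about 25 points (80% against 54.8%) appears only when the ends are crossed. What is missing is a detail that an analyst supplies correctly from the section's own inputs.

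The practical residue is a caution for interpretation: a study that closes at 50 has about 80% power only for changes of about 0.4 SD or more. These figures assume independent participants, complete pairs, normally distributed differences and an unadjusted 5% for each outcome.

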## 15.0 Data Safety Monitoring Plan

Not applicable

## 16.0 Adverse Events

Not applicable

# 17.0 Quality Assurance Procedures and Participant Confidentiality

Information about study subjects will be kept confidential and managed according to the requirements of the Health Insurance Portability and Accountability Act of 1996 (HIPAA). To ensure confidentiality all records will be on encrypted, password-protected computers (See section 7).

Quality assurance procedures for administration of the educational intervention include completion of a fidelity checklist to ensure that health educators are reviewing the material in consistent and complete manner. Health educators will be asked to track whether any portion of the educational slides was not reviewed, and will document reasons for non-completion.

## 18.0 Participant Informed Consent

See Section 9.0.

# 19.0 Appendices

- Appendix A: Informed Consent Form
- Appendix B: PowerPoint Presentation and Educational Brochure
- Appendix C: Pre/Post-Test Survey
- Appendix D: Sign in Sheet

